7.1.6 Analysis of Safety and Other Measures

Safety measures include AEs, ocular examinations and assessments (VA, slit-lamp biomicroscopy, IOP measurement), and skin irritation assessments.

The number and percentage of subjects reporting AEs during the study will be tabulated by MedDRA SOC and by preferred term within each organ. The AE tables will be separately presented by ocular and non-ocular. Ocular AEs will be tabulated by maximum severity and maximum relationship to treatment. For non-ocular AEs, tables will be generated in the same fashion of ocular AE tables, if necessary. System organ classes summary will be listed with eye disorders first, followed by SOCs listed in order of descending frequency for all subjects. Preferred terms will be listed in order of descending frequency within each SOC. Summaries and listings will be provided for subjects reporting SAEs, subjects experiencing AEs related to study medication, and subjects withdrawing due to an AE. The percentages of specific AEs between treatments may be analyzed using Fisher's exact test if they are extremely unbalanced between groups.

Slit-lamp biomicroscopy will be performed at baseline (pre-dose on Day 1) and just after patch removal on Days 8 ± 1 and 15 ± 1 . All biomicroscopy findings will be graded Normal, Abnormal (not clinically significant), or Abnormal (clinically significant) by the investigator. The frequency distribution (number and percentage) of findings in each treatment group at baseline will be tabulated along with the frequency distribution at each time point. The percentages of slit-lamp biomicroscopy findings between treatments may be analyzed by using Pearson's chi-Square test or Fisher's exact test, if necessary, at each time point.

Visual acuity, IOP, ocular comfort score, skin comfort score, and the patch adhesion assessment score will be summarized using descriptive statistics (number of subjects, mean, median, range, and standard deviation) at each time point. The SUN-131 1.5% TDS will be compared to the placebo TDS results at each time point. The changes from baseline (Day 1) will be calculated and the groups compared. A paired t-test will be used to compare the treatment groups at each time point. Additionally, a Wilcoxon signed-rank test may be used for analysis of the skin irritation scores if the distribution of data appeared to be not normally distributed. All statistical testing will be evaluated using a level of significance (α) of 0.05.

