Study Design	
This is a prospective multi-center, double-masked, randomized, placebo-controlled clinical trial. Subjects will be centrally randomly assigned in a 1:1 ratio to receive one of the following treatments in the affected eyelid:
 
SUN-131 1.5% TDS (n = 130) Placebo TDS (n = 130)
 
The randomization will be stratified by age group (<12 years, ≥12 years). All study drug will be worn for a minimum of 16 hours and a maximum of 24 hours each day for 14 days.
 
The following items will be assessed at screening/baseline and at 30 minutes to 1 hour after patch removal on Days 8 ± 1 and 15 ± 1.
 
 • Presence of a chalazion by examination (clinical assessment) • [REDACTED] • Erythema of the chalazion site itself as measured by a 5-point scale (0 = no sign of erythema, 1 = slight erythema, 2 = mild erythema, 3 = moderate erythema, 4 = severe erythema) • Pain in study eyelid and eye of the study eyelid related to chalazion as measured by Visual Analog Scale (VAS) of 100 mm 
Patient Reported Outcome (PRO) will be assessed by a self-evaluation diary of chalazion (present or absent), completed daily by the subjects from Day 1 through Day 15 ± 1.

Sample Size	Approximately 260 subjects will be randomized.
Study Population	Male or female subjects aged ≥ 6 years with a chalazion
Inclusion Criteria	
Subjects eligible to participate in the study must meet all of the following criteria:
 
 1. Subjects aged ≥ 6 years of either sex and of any race. 2. Subjects with a diagnosis of a single chalazion with visible granuloma in the study eyelid. Study eyelid may be either an upper or lower eyelid. 3. Subjects with a chalazion with the granuloma area (height x width) ≤ 36 mm² when measured by a caliper. 4. Subjects with chalazion erythema score of ≥ 1 (as graded on a 5-point scale: 0 = no erythema, 1 = slight erythema, 2 = mild erythema, 3 = moderate erythema, 4 = severe erythema). 5. Chalazion intended for study treatment present for no more than 21 days based on patient history on Day 1. 6. Normal eyelid function without active signs of eye/eyelid infection in either eye.

[figure not shown]

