Senju has more recently completed a Phase 2, multi-center, randomized, placebo-controlled clinical trial in adult subjects with a chalazion. Subjects were randomly assigned to receive either SUN-131 1.5% TDS or placebo TDS in a 1:1 ratio. All patches were worn for 16 ± 4 hours each day for 21 days. A total of 69 subjects were enrolled in the trial and 58 completed the trial. There were 11 subjects, 6 in the SUN-131 1.5% TDS group and 5 in the placebo TDS group, who discontinued the study for non-safety-related reasons. Of the 69 subjects enrolled, 68 received either the SUN-131 1.5% TDS or the placebo TDS and thus were evaluable for safety. A total of 35 subjects received at least one dose of active SUN-131 1.5% TDS, of which 29 subjects completed the study with all doses through Day 21. A total of 33 subjects received at least one dose of placebo TDS of which 29 subjects completed the study with all doses through Day 21.

Overall, the safety of the SUN-131 1.5% TDS was excellent with no clinically meaningful product-related adverse effects. There were no notable changes in VA, slit-lamp biomicroscopy, IOP, skin irritation or ocular and skin discomfort. Twenty-four (24) of 68 subjects (35.3%) experienced at least 1 TEAE in the study. Eight (8) subjects (11.8%) experienced TEAEs that were considered treatment-related by the investigator. The most frequently experienced TEAEs overall in the study were chalazion (3 subjects; 4.4%) and eye pruritus (3 subjects, 4.4%). Thus, the SUN-131 1.5% TDS demonstrated a good safety profile for the intended indication.

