7.1.1 Analytical Populations

- **Intent-to-Treat:** The ITT population will include all randomized subjects. All primary and secondary efficacy analyses are to be on the ITT population.
- **Modified Intent-to-Treat:** The mITT population will include all randomized subjects with at least one post-baseline primary outcome assessment. Results of the efficacy analyses based on the mITT population will be presented as a sensitivity analysis. Treatment assignments in the mITT population will be based on the treatment to which the subject was randomized.
- **Safety:** The safety population will include all randomized subjects who received the study drug. Treatment assignments in the safety population will be based on the treatment that was received (if different from the randomized treatment).
- **Per-Protocol:** The PP population will exclude from mITT population those subjects who have major protocol violations. Major protocol violations include violation of entry criteria, receiving the incorrect randomization, noncompliance with study drug administration (missing the study drug administration more than 80% of study drug or failure to apply the study drug for at least 5 days per week and miss more than 2 of 7 days of application), and the use of prohibited medications. Treatment assignments in the PP population will be based on the treatment that was received (if different from the randomized treatment).

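### An adverse-event p-value produced only when the arms already look extremely unbalanced cannot be read at face value against 0.05

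*Combined protocol and SAP*

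**What the plan says.** Section 7.1.6 makes the main AE output descriptive: "The number and percentage of subjects reporting AEs during the study will be tabulated by MedDRA SOC and by preferred term within each organ". Ocular AEs are also tabulated by maximum severity and relationship, and there are summaries and listings of serious AEs, related AEs and withdrawals due to AEs.

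It then adds an option. The percentages of specific AEs may be compared between treatments by Fisher's "exact test if they are extremely unbalanced between groups". The section closes with "All statistical testing will be evaluated using a level of significance (α) of 0.05".

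The text shown gives no numerical meaning to extreme imbalance, names no AE term in advance for testing, does not address multiplicity across terms, and plans no confidence interval for an AE difference. It does not call these p-values descriptive.

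**The concern.** The condition for running the test is the quantity that the test evaluates. Terms that look balanced get no test, and terms that look unbalanced may get one that is then held against 0.05. The reader of the report sees the selected p-values but not how many terms were looked over to find them. Two analysts who both follow the plan could report different sets of tests, because the trigger is a judgement made on the observed gap.

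At stake is how the safety results are read. Safety is part of the trial's stated objective (section 2). A small p-value for a term that split unevenly by chance would overstate the evidence of harm. The primary efficacy analysis is not touched.

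**Working it through.** The plan states no figure for AE testing, so there is none to reproduce. The calculation below measures what the trigger does to the p-values that get reported.

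**Inputs**
- Arm sizes: "SUN-131 1.5% TDS (n = 130) Placebo TDS (n = 130") in the synopsis and section 3.1.
- Denominator: "The safety population will include all randomized subjects who received the study drug" (section 7.1.1). I take this as all 130 per arm.
- Level: 0.05 (section 7.1.6). Sidedness is not stated for AE tests; I assume two-sided.
- Illustrative rate: 4.4% in both arms, from the Phase 2 summary in section 1.2: "The most frequently experienced TEAEs overall in the study were chalazion (3 subjects; 4.4%) and eye pruritus (3 subjects, 4.4"%). A rate of 10% is added as an assumption.
- Trigger: the plan gives no threshold. I assume the test is run when the counts differ by at least k subjects, with k = 5, 6, 8 or 10.

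**Step 1: smallest splits that reach 0.05.** Two-sided Fisher p-values at 130 per arm are 0.060 for 5 v 0, 0.030 for 6 v 0, 0.036 for 8 v 1 and 0.034 for 10 v 2. These are splits that a reader would be likely to call extremely unbalanced, so the trigger and the significance threshold largely pick out the same tables.

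**Step 2: effect of the trigger.** Let X and Y be independent Binomial(130, r) counts with the same r in both arms. Enumerate all pairs and compute

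P(p < 0.05 given tested) = P(|X − Y| ≥ k and p < 0.05) / P(|X − Y| ≥ k).

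At r = 4.4%:

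| Gap k that triggers the test | P(tested) | P(tested and p < 0.05) | Share of reported p-values below 0.05 |
|---|---|---|---|
| always tested | 1 | 0.0209 | 2.1% |
| 5 | 0.1706 | 0.0209 | 12% |
| 6 | 0.0949 | 0.0209 | 22% |
| 8 | 0.0237 | 0.0160 | 67% |
| 10 | 0.0045 | 0.0045 | 99.7% |

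At r = 10% the shares are 9%, 12%, 25% and 60%, against 3.0% when always tested. The stricter the reading of extreme imbalance, the closer a p-value below 0.05 comes to being certain once the test is run.

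**Step 3: what the trigger does not do.** The third column never exceeds 0.0209. A term that is tested and significant is a subset of the terms that would be significant if always tested, so the unconditional false-positive rate per term is not raised and stays below 5%. The fault lies in how a reported p-value is read.

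**Step 4: multiplicity, a separate matter.** If m independent null terms, each at 4.4%, were all tested with no trigger, the chance of at least one p < 0.05 would be 1 − (1 − 0.0209)^m: 19% for m = 10, 34% for m = 20 and 57% for m = 40. This depends strongly on the assumed event counts. Fixing the total per term, the null rejection probability is 0 at 5 events, 2.9% at 6, 1.4% at 7, 0.7% at 8 and 3.6% at 9. For 10, 20 or 30 terms that gives 26%, 45% and 59% at 6 events, but 7%, 13% and 19% at 8 events. None of these figures measures the trigger.

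**The case against.** The strongest reply is that little rests on this sentence. The wording is permissive, so perhaps no AE p-value will ever be produced. Counts and percentages appear for every term whatever the split, and nothing in the documents bases a safety conclusion on an AE p-value. All of that stands, and it is why the point is minor. It does not cure the rule: discretion used after seeing the gap is what makes a resulting p-value hard to interpret, and the plan holds that p-value against 0.05.

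Two stronger readings are tempting. A reader might infer that the trigger inflates the false-positive rate for each AE. It does not (Step 3), and the percentages in Step 4 would be the same if every term were tested unconditionally. A reader might also infer that an untested or non-significant term is to be taken as cleared. Section 7.1.6 says nothing of the kind, and the counts for such terms are still shown by arm. What is true is narrower: no interval accompanies them, so the table does not show what excess the data leave open.

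It can also be objected that intervals will be read as tests. That is fair and bears on the choice of method. At 5 v 0 the Newcombe 95% interval runs from 0.2 to 8.7 percentage points and excludes zero, where Fisher gives p = 0.060. Likewise, an incidence cut-off that applies in either arm would still depend on the split: at 2% of 130 (2.6, so 3 subjects), a four-subject term split 3 to 1 is shown and one split 2 to 2 is not.

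**Conclusion.** The concern holds in a limited form. Any AE p-value produced under the rule in section 7.1.6 is selected on the quantity it tests and cannot be taken at face value against 0.05. At a true rate of 4.4% in both arms, between 12% and 99.7% of such p-values would fall below 0.05 for assumed triggers of 5 to 10 subjects, against 2.1% if the term were always tested. These figures rest on 130 treated subjects per arm, two-sided testing, equal true rates and the assumed gap thresholds. The direction does not depend on the particular threshold among those tried; the size does.

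Screening many terms is a separate multiplicity problem, whose size depends on the number of terms and the event counts, neither of which the documents give. The point is limited to safety reporting and would be a worthwhile tidy-up, not a condition for the trial.

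**What to change.** Delete the imbalance trigger from section 7.1.6. In its place, for every system organ class and preferred term at or above an incidence cut-off pooled over both arms and fixed before unmasking, give n and % by arm and the risk difference with an exact 95% confidence interval. State that the intervals are descriptive and unadjusted for multiplicity. A cut-off of 2% of all subjects, for example, is 0.02 × 260 = 5.2, so 6 or more subjects in total. Because it uses the pooled count, how those subjects divide between arms cannot affect which terms are shown. Terms below the cut-off stay in the planned tables and listings.

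If the sponsor wishes to keep AE p-values, compute them for all terms that meet the pooled cut-off, label them descriptive and unadjusted, and exempt them from the 0.05 sentence.

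The cost is a change of wording, two more columns in the AE tables and the loss of an optional p-value. No new data are needed.

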1 INTRODUCTION

A chalazion, also known as a Meibomian gland lipogranuloma, is a cyst in the eyelid that is caused by a blocked Meibomian gland, in the upper or lower eyelid, that causes an inflammatory response. The Meibomian glands are responsible for excreting sebum and meibum that help lubricate the skin, eyelash hairs, and eyes. Chalazia are generally subacute dermal inflammations that are often uncomfortable and in rare cases can cause astigmatism that may require surgical treatment. Clinical signs and symptoms of a chalazion include swelling on the eyelid, eyelid tenderness, and irritation to the eye.

There are no current US FDA-approved products specifically to treat chalazion, however, typical treatments range from simple interventions, such as hot compresses, to more serious chalazion that require treatment with an injection of corticosteroid into edema or require surgical removal of the chalazion. Given no specific product is approved to target the chalazion in the eyelid subdermal region, off-label treatments with corticosteroid ophthalmic ointments and eye drops are common. These treatments often expose the eye to significant doses of corticosteroid and fail to adequately target the Meibomian gland, thus giving a less optimal effect and more risk of AEs like increase of IOP induced by steroid eye drops.

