The anti-inflammatory and immunosuppressive effects of glucocorticoids, such as [REDACTED], rely on several molecular mechanisms, that have been elucidated by basic research (1). Three main mechanisms include direct effects on gene expression by the binding of glucocorticoid receptors to glucocorticoid-responsive elements (i.e., the induction of annexin I and mitogen-activated protein kinase phosphatase 1 [MKP-1]), indirect effects on gene expression through the interactions of glucocorticoid receptors with other transcription factors (i.e., NF- κ B and activator protein 1), and glucocorticoid receptor-mediated effects on second-messenger cascades (i.e., the PI3K–Akt–eNOS pathway). Unfortunately, because some of these mechanisms are also involved in systemic physiologic signaling rather than inflammatory signaling, the therapeutic effects of systemic glucocorticoids in inflammation are often accompanied by clinically significant side effects when given in the systemic circulation. Given that the target indication is a chalazion, targeting the application of [REDACTED] to the site of inflammation is considered the most effective approach with the least potential for systemic or ocular side effects.

The SUN-131 ([REDACTED]) TDS is designed for local delivery of a corticosteroid, [REDACTED], to the upper or lower eyelid. This TDS is specially engineered to gently adhere to the eyelid and is shaped to fit the contours of the eye. The backing and adhesives used are also designed to allow removal of the patch without causing irritation and to be flexible for adequate comfort. Thus, targeted local delivery of [REDACTED] to treat the chalazion can be achieved from this unique transdermal design without significant exposure of the active agent to the eye, as with ointment or drops. Thus, this is considered a dermal application of a

TDS to treat a local extra-ocular disease in the eyelid. The low local dose also will minimize any potential for systemic exposure and minimize exposure to the eye.

[Redacted text block]

[Redacted text block]

[Redacted text block]

[Redacted text block]

1.1 Phase 1 Clinical Evaluation of the SUN-131 TDS:

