4.1.2 Exclusion Criteria

Subjects who meet the following criteria are not eligible to participate in this study:

1. Chalazion that has atypical features (a recurring chalazion at the same spot, abnormal surrounding lid tissue, associated loss of tissues).
2. History of chalazion incision and curettage in study eyelid.
3. Chalazion at the eyelid margin (≤ 2 mm distant from the edge of the study eyelid margin).
4. Multiple chalazia in the study eyelid or in any non-study eyelid(s). A single chalazion in any non-study eyelid(s) is(are) allowed. .
5. Chalazion on an eyelid that was previously screen failed. Re-screening of the same subject is allowed only once.
6. Chalazion on the opposing eyelid (i.e. same side) of an eyelid which was previously enrolled. Re-entry of the same subject is allowed only once.
7. Active ocular or eyelid infection (bacterial, viral, or fungal), any ocular or eyelid condition in the study eyelid/eye of study eyelid that in the investigator's opinion could affect the subject's health or the study parameters.
8. Presence of hordeolum in any one eyelid.
9. An abnormal skin condition on the study eyelid region (e.g., eczema, psoriasis, atopic dermatitis, etc.) where the study drug will be applied.
10. Intraocular pressure greater than 22 mmHg in either eye.
11. Diagnosed with glaucoma in either eye.
12. History of steroid-induced elevation of IOP.
13. Use of systemic (intravenous, intramuscular, oral), ophthalmic, or dermatological corticosteroids or immunosuppressant within 4 weeks prior to Day 1 and throughout the study period. Inhalant, intranasal intra-articular, and perianal steroids are permitted.
14. Use of systemic or ophthalmic azithromycin in either eye within 5 weeks prior to Day 1 and throughout the study period, use of other systemic or ophthalmic macrolides (e.g. erythromycin, clarithromycin, etc.) in either eye within 2 weeks prior to Day 1 and

throughout the study period, and use of tetracyclines (e.g. tetracyclines, doxycyclines, etc.) in either eye within 2 weeks prior to Day 1 and throughout the study period.

15. Use of periocular or intraocular corticosteroid injection or corticosteroid depot in either eye within 9 weeks prior to Day 1 and throughout the study period.
16. Female subjects who are pregnant or lactating.
17. Known allergy or sensitization to the test article or any formulation components.
18. History or evidence of ocular surgery in either eye or eyelid within the past 3 months.

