7 STATISTICAL METHODS AND DETERMINATION OF SAMPLE SIZE

7.1 Statistical and Analytical Plans

All data collected on CRFs will be presented in data listings. The primary and secondary endpoints for this trial will be evaluated using the Intent-to-Treat (ITT) population with the Modified Intent-to-Treat (mITT) performed as a sensitivity analysis. The safety analyses will be carried out using the safety population. Comfort scores (ocular, skin, and the average of both), patch adhesion, and residual drug content will be analyzed using the ITT population (and mITT and Per-Protocol [PP] populations if there are subjects with protocol deviations or incomplete data). In general, the grade for each measure in each eye will be used for analysis of treatment effects unless otherwise specified. All analyses will be conducted in a validated instance of SAS 9.1 or higher.

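### Section 7.1.6 summarises IOP with continuous statistics and tests it on means; it plans no count of subjects with a defined IOP rise or level and names no analysis eye

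*Combined protocol and SAP*

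**What the plan says.** Section 7.1.6 lists IOP among the safety outcomes: "Safety measures include AEs, ocular examinations and assessments (VA, slit-lamp biomicroscopy, IOP measurement), and skin irritation assessments". It then groups IOP with visual acuity, the comfort scores and patch adhesion: "Visual acuity, IOP, ocular comfort score, skin comfort score, and the patch adhesion assessment score will be summarized using descriptive statistics". The statistics are "number of subjects, mean, median, range, and standard deviation) at each time point". For change it adds: "The changes from baseline (Day 1) will be calculated and the groups compared". The statistics to be shown for change are not itemised. The test named is a paired t-test at the 0.05 level.

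In the same section, slit-lamp findings receive a table of numbers and percentages by arm and time point. IOP does not.

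On the choice of eye, Section 5.2 has all ocular safety measurements made in both eyes. Section 7.1 gives only a general rule: "the grade for each measure in each eye will be used for analysis of treatment effects unless otherwise specified". Section 7.1.6 does not say which eye enters the IOP comparison.

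On background, the Introduction says that the system "is designed for local delivery of a corticosteroid", and it criticises conventional steroid treatment for "more risk of AEs like increase of IOP induced by steroid eye drops". Section 4.1.2 excludes "Intraocular pressure greater than 22 mmHg in either eye", diagnosed glaucoma, and a history of steroid-induced IOP elevation.

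**The concern.** The exclusion criteria show that the sponsor regards a pressure response to steroids as something that differs between individuals. Exclusion by history cannot remove subjects whose response has never been tested. If such a response occurs in a few subjects, the useful question is how many per arm had a rise of a stated size. The planned IOP analysis does not answer it. A mean and a t-test on means respond weakly to a few large values.

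Safety is part of the trial's stated objective. The report could show nearly equal mean changes without saying whether two treated subjects or eight had a marked rise. The unnamed eye adds to this: only one eyelid is treated, so the study-side and fellow eyes carry different information about a local effect.

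**Working it through.** **No plan figure to reproduce.** The documents give no IOP effect, SD or power. Section 7.1.7 has no visible text in the public copy, which is not held against the plan. What follows is an illustration.

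**Inputs**
- From the documents: 130 subjects per arm (Section 3.1); entry IOP at most 22 mmHg (Section 4.1.2); significance level 0.05 (Section 7.1.6), taken as two-sided.
- Assumed: a share f of active subjects rises by 10 mmHg and all others have mean change 0; SD of change s = 2.5 to 3.0 mmHg; baseline IOP has mean 14 to 16 and SD 3 mmHg, truncated at 22.
- The arms are independent, so the comparison of means is modelled as a two-sample t-test. A paired test does not fit two parallel arms; that is a separate point.

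**1. Comparison of means, f = 5%**
- Expected number affected: 130 × 0.05 = 6.5. Shift in the arm mean: 0.05 × 10 = 0.5 mmHg.
- Variance of change in the active arm: s² + f(1−f) × 10² = s² + 4.75.
- s = 2.5: variances 11.0 and 6.25, average 8.625; SE = √(2 × 8.625/130) = 0.364; 0.5/0.364 = 1.37; power ≈ Φ(1.37 − 1.96) = 0.28.
- s = 3.0: variances 13.75 and 9.0, average 11.375; SE = √(2 × 11.375/130) = 0.418; 0.5/0.418 = 1.20; power ≈ Φ(1.20 − 1.96) = 0.22.
- Simulation, which allows for the skewed mixture, gives about 0.21 to 0.27.
- Sensitivity by formula, for s from 2 to 3.5: 0.36 down to 0.18 at f = 5%; 0.11 down to 0.07 at f = 2%; 0.64 down to 0.37 at f = 8%.

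**2. Count of subjects with a rise from baseline, f = 5%**

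Placebo share: P(Z > c/s). Active share: 0.05 × P(Z > (c−10)/s) + 0.95 × P(Z > c/s).

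| Cut c (mmHg) | s | Placebo | Active |
|---|---|---|---|
| 6 | 2.5 | 0.8% | 5.5% |
| 6 | 3.0 | 2.3% | 6.7% |
| 8 | 2.5 | 0.1% | 4.0% |
| 8 | 3.0 | 0.4% | 4.1% |

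Simulated power of a two-sided Fisher test over these four cases is about 27–46%. The cuts are illustrative only.

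**3. Count of subjects above 22 mmHg, f = 5%**

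Subjects may enter at up to 22 mmHg, so measurement variation alone takes about 2–7% of placebo subjects over that level at a visit. Fisher power falls to about 14–19%, below the t-test.

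**4. Rarer responses**

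Take an idealised count in which every affected subject crosses the cut and nobody on placebo does. Significance then needs at least 6 affected in the active arm (5 against 0 gives p = 0.060). The chance of 6 or more is 5% at f = 2%, 20% at f = 3% and 64% at f = 5%. Below 5% affected, a test on counts is also weak.

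**5. What the range would show**

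If the range of the change is reported, the active-arm maximum is 10 mmHg or more in about 95–97% of simulated trials at f = 5%, and 73–80% at f = 2% (s from 2 to 3.5). The plan, however, itemises the range for values at each time point, not for change. A subject rising from 12 to 22 mmHg need not alter an arm's maximum value.

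**The case against.** The plan is not blind to IOP outliers. It reports median, range and SD as well as the mean. Section 7.1 promises listings of all CRF data. Section 6 defines an adverse event widely enough to include a pressure rise, and 7.1.6 tabulates ocular events by preferred term, severity and relationship, with Fisher's test available for marked imbalance. The medical monitor reviews data periodically. A reader might infer that IOP is analysed only as group means and that a subgroup would be averaged away. That is true of the mean and the t-test, but not of the range, listings or event tables.

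These routes still leave a gap. The range gives one extreme value per arm, listings do not summarise by arm, and no IOP threshold triggers an adverse event. Event counts therefore depend on investigator judgment at up to 67 sites.

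A reader might also infer that treated and untreated eyes will be pooled, diluting any local effect. The documents do not say so. The rule in 7.1 refers to each eye and reads more naturally as analysis by eye. What stands is that 7.1.6 leaves the eye unnamed.

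The prior evidence is reassuring but limited. The Introduction attributes the IOP risk to eye drops and says that the patch is designed to avoid significant exposure of the eye. Phases 1 and 2 reported no notable IOP changes, and Phase 2 used the same strength for 21 days. But Phase 2 had 35 subjects on active. With a true rate of 5%, the chance of seeing none affected is 0.95³⁵ = 17%; at 2% it is 0.98³⁵ = 49%. Both trials enrolled adults, whereas this one enrols from age 6.

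The absence of a data monitoring committee does not bear on which final tables are produced.

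**Conclusion.** The point holds as a gap in reporting that is cheap to close. For a locally applied corticosteroid, the plan specifies continuous IOP summaries and a test on means. It defines no IOP rise or level to be counted and does not name the analysis eye.

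The gain in detection is moderate and depends on the cut. At 5% affected with a 10 mmHg rise, power goes from about 21–27% (t-test) to about 27–46% (rise of at least 6 or 8 mmHg). A count above 22 mmHg alone does worse, at about 14–19%. At 2–3% affected the benefit is descriptive: the number of subjects per arm, with its uncertainty. The share affected, size of rise, SDs and baseline distribution are assumptions, and the documents do not say that responders are a minority. The results do not support a claim that the trial as planned would conceal an IOP effect.

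**What to change.** In Section 7.1.6:
- Name the study-side eye as the IOP analysis eye and report the fellow eye separately.
- Add a table, by arm and visit, of the number and percentage of subjects with a rise from baseline of prespecified sizes (the main display) and of those above a prespecified level. The sponsor should choose and justify the thresholds before unmasking.
- Give the risk difference between arms with a 95% CI.
- Keep n, mean, median, range and SD as descriptive summaries, and state that they are given for change as well as for values.

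The cost is one extra table and its programming. No new data, visits or subjects are needed.
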